2.1.3 Inferential statistics

All statistical comparisons will be made using two-sided tests at the 0.05 significance level unless specifically stated otherwise. As this is a proof-of-concept study, no correction method for multiple testing is foreseen. P-values should thus be interpreted accordingly.

Difference between MVA-NP+M1 and placebo in AUC (qPCR vAUC - primary analysis, culture vAUC, overall, local and general SSC AUC) and peak viral shedding/symptoms will be analysed using a Mann-Whitney U test. Additionally, adjusted difference between MVA-NP+M1 and placebo in AUC (qPCR vAUC, culture vAUC and overall SSC AUC) will be analysed using an ANCOVA model with treatment, sex, time since vaccination (see section 4.6.2) and challenge cohort as covariates.

Difference between MVA-NP+M1 and placebo in attack rate and virologically confirmed ILI will be analysed using a Fisher exact test.

Time to parameters will be analysed using Kaplan-Meier time to event analysis, with a log-rank test to compare MVA-NP+M1 and placebo.

Difference between MVA-NP+M1 and placebo in total days of fever will be tested using a zero inflated Poisson model.

Difference between MVA-NP+M1 and placebo in total mucus production will be tested with a t-test. Normality will be tested using a Shapiro-Wilk test. In case normality or homogeneity of variances assumption are not valid, a Mann-Whitney U test will be used.

Difference between MVA-NP+M1 and placebo in overall SSC changes from baseline will be analysed using a mixed model for repeated measurements (MMRM). The

	Statistical Analysis Plan	
FLU010	Final analysis	Final 3.0 of 15JUN2020

model will include treatment, sex, challenge cohort, timepoint and treatment by timepoint interaction terms as fixed effects, with baseline value and time since vaccination (see section 4.6.2) as covariates. Within-subject correlation will be modeled by assuming an unstructured (UN) covariance matrix for the error terms. If the model does not converge upon using UN, the following covariance structures will be tested for convergence (in order): heterogeneous Toeplitz (TOEPH), heterogeneous autoregressive first order (ARH(1)), heterogeneous compound symmetry (CSH), Toeplitz (TOEP), autoregressive first order (AR(1)) and compound symmetry (CS).

A similar MMRM model will be used for viral load (qPCR and culture) actual values, without the baseline covariate.

ANCOVA and MMRM models contain time since vaccination and challenge cohort, which are potentially highly correlated. This will be assessed by calculating the variance inflation factor in a regression model. In case of multicollinearity (max(VIF) > 10), challenge cohort will be dropped from the models.

No adjustment will be made for multiplicity

SAS code can be found in section 9.1.

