9.2 DETERMINATION OF SAMPLE SIZE

The sample size was chosen to have sufficient power to detect a 30% difference in the vAUC, assuming a drop out of approximately 15-20% from the vaccination group. Since there is 15% over-enrolment during the vaccination phase compared to challenge, it is assumed that in a worse-case scenario a 25% reduction, or that the final numbers to undergo challenge per group could be as low as 72 MVA-NP+M1 and 48 Placebo recipients. The placebo vAUC data were estimated using qPCR data accumulated during two previous challenge studies, where vAUC was calculated using the trapezoidal rule. The allocation ratio is chosen not at 2:1 (which would be 80:40), but rather at 80:54 to ensure sufficient placebo recipients within each challenge period to adequately assess the take rate of the challenge for that given cohort. Sample sizes of 80 and 54 participants in the MVA-NP+M1 and placebo groups, respectively, will yield approximately 90% power to detect at least a 22% difference in vAUC at a two-sided, alpha=0.05 level. If enrolment is lower than anticipated, approximately two-thirds of the planned sample size will still yield at least 80% power to detect a 30% difference in vAUC (two-sided alpha = 0.05).

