- Duration of viral shedding (hours) = (datetime of first negative swab following the last positive swab - datetime of first positive of two positive swabs within 2 consecutive days)/(60*60)
 - Duration will be rounded as detailed in section 5.3.4
 - All time points (including unscheduled time points) from day 2 to day 10 will be considered.
 - Subjects not having at least two positive swabs (within 2 consecutive days) will be excluded from this analysis (duration of viral shedding not calculated).
 - The end of viral shedding is defined as two consecutive negative swabs not followed by a positive swab. If this does not occur, the end of viral shedding will be set to the last viral load assessment.
 - This endpoint will be derived for both qPCR and culture
- vAUC based on culture values will be derived following the same rules as for the primary endpoint

	Statistical Analysis Plan	
FLU010	Final analysis	Final 3.0 of 15JUN2020

- Rate of virologically confirmed ILI: virologically confirmed ILI is defined as having a positive swab and a respiratory or flu-like symptom occurring on two consecutive days
 - A positive swab is defined as a positive qPCR.
 - All time points (including unscheduled time points) from day 2 to day 10 will be considered.
 - Positive swab and flu-like symptom have to occur on the same two consecutive days.
 - Respiratory or flu-like symptom can be any of the following signs or symptoms collected on the SSC: runny nose, sneezing frequency, sinus pressure/pain or facial pain, sore throat, difficulty swallowing, teary/watery eyes, painful eyes, aversion to light, dry cough, productive (wet) cough, difficulty breathing/tight chest, feverish, chills or shivering, sweating, lymphadenopathy
- Overall SSC AUC
 - AUC will be derived following the same rules as for the primary endpoint and rounded as detailed in section 5.3.4
 - SSC AUC will be calculated using the overall SSC score
 - Overall SSC score = arithmetic mean of all items
 - As lymphadenopathy is assessed only once a day, the value collected for that day will be used for both the AM and PM assessments in the calculation of SSC score.
 - Missing items will be handled as detailed in section 5.3.1

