9. APPENDICES

9.1 SAS CODE

Mann-Whitney U test

```
proc npar1way data=dataset wilcoxon;  
  var AVAL;  
  class TRTP;  
run;
```

Fisher exact test

```
proc freq data= dataset;  
  table AVAL *TRTP/fisher;  
run;
```

Survival analysis with log rank test

```
proc lifetest data= dataset method=KM;  
  time AVAL * CENSOR(1);  
  strata TRTP / test=logrank;  
run;
```

Zero-inflated Poisson

```
proc hpfmm data=dataset;  
  class TRTP;  
  model AVAL = TRTP / dist=Poisson ;  
  model + / dist=Constant;  
run;
```

T-test with checking model assumptions of homogeneity of variances and normality

```
proc glm data= dataset order=internal;  
  class TRTP;  
  model AVAL = TRTP;  
  output out = norm r = resid;  
  means TRTP / hovtest;  
quit;
```

	Statistical Analysis Plan	
FLU010	Final analysis	Final 3.0 of 15JUN2020

```
ods select testsfornormality;  
proc univariate data=norm normal; var resid; run;
```

ANCOVA model

```
proc mixed data=dataset;  
  class TRTP CHCOHORT SEX;  
  model AVAL = TRTP CHCOHORT VACTIME SEX/solution;  
  lsmeans TRTP / diff=control('Placebo') cl;  
run;
```

Multicollinearity testing

```
proc reg data=dataset;  
  model AVAL = TRTP CHCOHORT VACTIME SEX/selection=none vif;  
run;
```

MMRM model

```
proc mixed data=dataset;  
  class USUBJID ATPTN TRTP CHCOHORT SEX;  
  model LGAVAL= TRTP ATPTN ATPTN*TRTP CHCOHORT VACTIME SEX /  
  ddfm=KR S;  
  repeated ATPTN /subject= USUBJID type=UN;  
  lsmeans ATPTN*TRTP / cl pdiff alpha=0.05;  
run;
```

Note: if covariance structure other than UN (unstructured), then ddfm = BW should be used as option to handle degrees of freedom.

Multiple imputation

```
proc mi data= inputdata NIMPUTE=100 SEED=22087 OUT=mnardata;  
  class TRTP;  
  var LGAVALTP1- LGAVALTP22;  
  fcs reg;  
  mnar model (LGAVALTP1- LGAVALTP22)/modelobs=( TRTP ='Placebo'));  
run;
```

	Statistical Analysis Plan	
FLU010	Final analysis	Final 3.0 of 15JUN2020

Permutation-based Resampling Method

```
%macro vect(len=, place=);  
  %do nn=1 %to &len;  
    %if(&nn ^= &place) %then 0;  
    %if(&nn = &place) %then 1;  
  %end;  
%mend vect;  
  
%macro mymult(data_in=, k=);  
  proc multtest data=&data_in perm n=100000 order=data stepperm out=permresults  
  seed = 1;  
  by usbjid atpt;  
  class well;  
  test mean(count/upper);  
  %do peps = 1 %to &k;  
    contrast "peptide&peps" -1 %vect(len=&k, place=&peps);  
  %end;  
  run;  
%mend mymult;  
  
%mymult(data_in=inputdataset,k=2)  
data respstat;  

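### The supportive ANCOVA of overall SSC AUC leaves out the pre-challenge symptom score that the repeated-measures model of the same score adjusts for; the cost is a little precision and consistency, not bias.

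*SAP*

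**What the plan says.** SAP 2.1.3 uses one ANCOVA for three outcomes (qPCR vAUC, culture vAUC and overall SSC AUC). The adjusted difference "will be analysed using an ANCOVA model with treatment, sex, time since vaccination (see section 4.6.2) and challenge cohort as covariates". The code in SAP 9.1 has the same four terms: "model AVAL = TRTP CHCOHORT VACTIME SEX/solution".

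The same section fits an MMRM to the change from baseline in overall SSC, "with baseline value and time since vaccination (see section 4.6.2) as covariates". For viral load it explicitly drops the baseline term. The T-cell and antibody ANCOVAs in SAP 2.2.3 also adjust for baseline.

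A pre-inoculation symptom score should be available. SAP 5.2.2 takes the challenge baseline as the last non-missing value before inoculation, the score card in SAP 9.2 starts on Day 1, and SAP 5.3.1 places the first scheduled score one minute before challenge when it has to be imputed.

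On the outcome itself, SAP 2.1.2.2 says "SSC AUC will be calculated using the overall SSC score", so the raw score is integrated and not its change. Protocol 9.1.2.2 treats symptom AUC as a key secondary endpoint and compares it by a Mann-Whitney test. The ANCOVA is additional and is reported in tables 14.2.3.1.3 (flagged for topline) and 14.2.3.1.4 (multiple imputation).

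**The concern.** Where a baseline measurement of the outcome has been collected, the SAP's other adjusted efficacy and immunogenicity models use it. The overall SSC AUC is the exception. It shares a formula with two virological AUCs, and the SAP's own viral-load MMRM carries no baseline term, so the omission looks inherited rather than chosen.

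A participant who has a mild complaint on the morning of inoculation, and keeps it, has a higher AUC for reasons unrelated to the challenge. Without the baseline score in the model, that predictable part stays in the residual, and a chance difference between arms in baseline scores goes uncorrected. The MMRM of the same score would correct for it, so the two adjusted analyses could differ for a reason unrelated to the vaccine.

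**Working it through.** **Inputs.** From the documents: "Sample sizes of 80 and 54 participants in the MVA-NP+M1 and placebo groups, respectively" (Protocol 9.2); "All statistical comparisons will be made using two-sided tests at the 0.05 significance level unless specifically stated otherwise" (SAP 2.1.3); 8 challenge cohorts (SAP 4.6.1); 4+2+3+3+4+12 = 28 symptom items (SAP 2.1.1). Not in the documents: the SD of symptom AUC, and its correlation (rho) with the pre-challenge score. Rho is assumed and shown over a range; strictly it is the correlation after the other covariates.

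**1. The plan's own figure.** The only stated power is for vAUC: the planned sizes "will yield approximately 90% power to detect at least a 22% difference in vAUC at a two-sided, alpha=0.05 level". Protocol 9.2 adds "The placebo vAUC data were estimated using qPCR data accumulated during two previous challenge studies", but prints no SD. The figure can therefore only be inverted, not reproduced: CV = 0.22 / [(1.960 + 1.282) × √(1/54 + 1/80)] = 0.22 / (3.242 × 0.1761) = 0.385. This concerns vAUC and does not test the present point. No power is stated for symptom AUC.

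**2. What the covariate is worth.** The planned model uses 11 parameters (intercept, treatment, sex, time since vaccination, 7 cohort contrasts), leaving 134 − 11 = 123 residual df, or 122 with baseline added. The ratio of interval widths, new to planned, is

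(t₀.₉₇₅,₁₂₂ / t₀.₉₇₅,₁₂₃) × √(1 − rho²) × √(1 + 1/122).

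Power is by normal approximation for an effect that has 80% power without baseline: Φ(2.802/√(1 − rho²) − 1.960).

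| rho (assumed) | interval width ratio | 80% power becomes |
|---|---|---|
| 0 | 1.004 | 80.0% |
| 0.1 | 0.999 | 80.4% |
| 0.2 | 0.984 | 81.6% |
| 0.3 | 0.958 | 83.6% |
| 0.4 | 0.920 | 86.4% |

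**3. Which rho is plausible.** Scenarios were simulated with 5–40% of participants having 1–3 total baseline points, 25–100% of that contribution persisting over 240 h, and the rest of the AUC having mean 40 and SD 35 score-hours (all assumed). Rho ran from 0.03 to 0.26. At 0.26 the width ratio is √(1 − 0.0676) × 1.0042 = 0.970, a gain of about 3%.

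**4. Why persistence matters.** One grade 1 item lasting 240 h adds 240/28 = 8.6 score-hours. If present only at the pre-challenge assessment, it adds about 6/28 = 0.2, because that point carries about 6 of 240 h under 12-hourly scoring. The window itself can be read two ways: SAP 2.1.2.2 borrows the primary-endpoint rules (Day 2 to Day 10), while SAP 5.3.1 runs from just before challenge to challenge plus 11 days. Under either reading the baseline score can predict AUC only to the extent that symptoms persist.

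**5. Bias.** In 4,000 simulated trials of 80 against 54 at each rho, the mean error of the treatment estimate was within 0.003 SD of zero with or without baseline. The standard errors, without and with baseline, were 0.178 and 0.179 at rho 0, and 0.177 and 0.170 at rho 0.3.

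**The case against.** The strongest reply is that little depends on this. The ANCOVA supports a Mann-Whitney test on a secondary endpoint, and a baseline-adjusted symptom analysis already exists in the MMRM. This stands, and it sets the weight of the point.

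Baseline scores should also be low. Challenge entry excludes ILI symptoms, fever, a positive viral PCR and recent rhinitis medication (Protocol 4.3), and study entry excludes hay fever and clinically significant seasonal rhinitis (Protocol 4.2). Six items, tiredness among them, are asked only when at least two other symptoms reach grade 2 (SAP 2.1.1), so isolated mild tiredness cannot enter the score. This stands too and points to a small rho. But a Day -2 or Day -1 admission check does not require zero on every item on Day 1.

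The covariate is measured after randomisation. That has little force: it is taken at least 6 weeks after vaccination, and the SAP already adjusts for it in the MMRM.

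Three stronger readings are tempting but unsupported:

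- **That the omission makes pre-existing symptoms count as influenza.** They count because the raw score is integrated. The covariate would leave every AUC value, and the Mann-Whitney test, unchanged.
- **That the comparison is biased.** Under randomisation with blinded scoring, background symptoms are expected equally in both arms.
- **That the loss is material.** A rho of 0.2 to 0.4 would be worth 134/0.96 − 134 = 6 to 134/0.84 − 134 = 26 participants, but nothing in the documents supports that range.

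**Conclusion.** The point holds as a minor one. The ANCOVA of overall SSC AUC omits an available pre-challenge score in both text and code, while the MMRM of that score includes it and no reason is stated. The issue is precision, chance imbalance and consistency.

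Adding the score makes the interval about 0.4% wider if rho is 0 and 8% narrower if rho is 0.4, with about 3% or less most plausible. The size rests on an assumed rho, on all 134 planned participants being analysed, and on challenge cohort staying in the model. The absence of bias rests on randomisation and on challenge entry not depending on arm. The primary vAUC analysis is unaffected.

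**What to change.** In SAP 2.1.3 and in the SAP 9.1 code, add the challenge-baseline overall SSC score (last value before inoculation, SAP 5.2.2) as a covariate in the ANCOVA of overall SSC AUC and in its multiple-imputation version (tables 14.2.3.1.3 and 14.2.3.1.4). Leave the two vAUC models and all Mann-Whitney tests unchanged. Because table 14.2.3.1.3 is a topline table and topline results are unblinded at group level before database lock (SAP 1.5), the change should be fixed before those results are seen. The cost is one model term and one degree of freedom; no new data are needed.

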Challenge agent dose levels increased per cohort and dosing started at a titre of approximately 10^5 TCID₅₀ (50% tissue culture infective dose/mL). In vivo toxicity, as determined by the established ferret model for Influenza A pathogenesis, suggested that A/Belgium/4217/2015 (H3N2) could be used at similar dosing titres (starting from 10^5 TCID₅₀/mL to 6.76×10^6 TCID₅₀/mL) as those previously used in human challenge trials. Based on international literature, comparing HI titres to MNT, a provisional cut-off for participant inclusion based on a MNT of ≤ 20 was chosen. Since the influence of low MNT (≥ 10) was unknown, volunteers with low MNT were equally distributed over the cohorts

While the lower bound of the required attack rate (>60%) was reached in all cohorts, none of the participants experienced an SAE or cytokine-related AE during the study even at the highest inoculation dose tested. The observed attack rate in all cohorts was well above the lower bound of the required attack rate. The signs and/or symptoms of Influenza infection similar to community acquired disease. Taken together, the data from the first in human dose escalation study show that A/Belgium/4217/2015 (H3N2) is a truly wild-type Influenza A H3N2 strain which, when used as challenge agent, results high attack rates and significant host changes with relatively low variation in virological, haematological, clinical laboratory and symptom efficacy parameters. The choice of challenge dose is dependent on several factors but an intermediate dose (10^6 TCID₅₀/mL) in volunteers with MNT ≤ 10 is adequate given the relatively low variation of essential efficacy parameters observed. Combining all data from further and ongoing studies, the attack rate for this dose with those participants with MNT ≤ 10 has been approximately 90%. Increasing this cut-off to < 20 should have a minimal effect on the predicted attack rate based on previous evidence.

Non-Clinical Studies

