3.2 DISCUSSION OF STUDY DESIGN

Dose Selection

The dose of MVA-NP+M1 to be used in this study will be 1.5×10^8 pfu (4.3×10^8 TCID₅₀) 0.5 mL administered intramuscularly, based on previous Phase 1 and 2a clinical trials, which have shown the vaccine is safe and immunogenic at this dose (FLU001, FLU002, FLU003, FLU004 and FLU005). Participants received the proposed 1.5×10^8 pfu dose in FLU001 which was less reactogenic and better tolerated than the 2.5×10^8 pfu used in one group. The immune responses were not significantly different between the two doses. The 1.5×10^8 pfu dose was thus chosen to balance reactogenicity and immunogenicity.

Placebo Control

Placebo saline control given as 0.5 mL intramuscularly in the deltoid will be used to establish the frequency and magnitude of solicited and non-solicited adverse events, as well as to control for the laboratory and clinical assessments used as endpoints. All such recordings will be performed in a blinded fashion.

Dose of challenge agent

The choice of challenge dose is dependent on several factors but an intermediate dose (10^6 TCID₅₀/mL) in volunteers with MNT <20 is adequate given the relatively low variation of essential efficacy parameters observed. Combining all data from previous and ongoing studies, the attack rate for this dose with those participants with MNT <20 has been approximately 83%.

Randomization and Blinding

Randomization will be used to avoid bias in the assignment of participants to treatment, to increase the likelihood that known and unknown participant attributes (e.g., demographic and baseline characteristics) are evenly balanced across treatment groups, and to enhance the validity of statistical comparisons across treatment groups. Participants are blinded to study allocation.

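### The supportive ANCOVA and MMRM omit screening MNT, a required pre-vaccination value; adding it is nearly free and probably gains a little precision

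*SAP*

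**What the plan says.** **Models.** SAP 2.1.3 makes the primary comparison unadjusted: AUCs and "peak viral shedding/symptoms will be analysed using a Mann-Whitney U test". In addition it plans an "ANCOVA model with treatment, sex, time since vaccination" and challenge cohort as covariates. For the symptom-score MMRM, the "model will include treatment, sex, challenge cohort, timepoint and treatment by timepoint interaction terms as fixed effects", with the baseline score and time since vaccination as covariates. For viral load, "A similar MMRM model will be used for viral load (qPCR and culture) actual values, without the baseline covariate". The ANCOVA code in SAP 9.1 agrees with the text: "model AVAL = TRTP CHCOHORT VACTIME SEX/solution". No titre term appears in either place.

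**Titre.** Protocol 3.1 and 4.1 require MNT <20 for enrolment. Protocol 7.1.1 requires the test within 6 weeks of vaccination and allows a result from another protocol. SAP 2.2.1 lists MNT at screening, challenge Day -1 and Day 28.

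**Attack rates.** Protocol 1.1 states: "Combining all data from further and ongoing studies, the attack rate for this dose with those participants with MNT" at or below 10 has been about 90%. Protocol 3.2 states: "Combining all data from previous and ongoing studies, the attack rate for this dose" has been about 83% for MNT <20. Protocol 1.1 adds that moving the cut-off to <20 should have a minimal effect. The rationale for version 5.0 says it should not affect take and that a twofold step lies within assay variability.

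**Role of the ANCOVA.** Under SAP 2.1.4.1 the primary table gives descriptive statistics and a p-value. The ANCOVA table gives the between-arm difference in vAUC with a 95% CI.

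**The concern.** A non-detected sample enters vAUC as log10 = 0 (SAP 5.3.3), so vAUC depends heavily on whether infection takes. If titre to the challenge strain predicts take, leaving it out widens the confidence interval of the adjusted vAUC difference and leaves chance imbalance in titre between arms uncorrected.

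Randomisation is not stratified (Protocol 5.5), so nothing else in the design balances titre. In the first challenge study with this strain, volunteers with low titres were spread evenly over the cohorts because their influence was unknown (Protocol 1.1). Sex is adjusted for although the documents report no attack rate by sex. Attack rates are reported by titre, yet titre is not adjusted for.

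**Working it through.** **1. The plan's own power figure.** Protocol 9.2 gives about 90% power for a 22% difference with 80 and 54 participants. No SD is stated, so the figure cannot be reproduced. It can only be solved backwards (normal approximation, two-sided 0.05): CV = 0.22 / [(1.960 + 1.282) × √(1/80 + 1/54)] = 0.22 / (3.242 × 0.1761) = 0.385.

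**2. What the two attack rates would imply.** Take both at face value and let *s* be the share in the added band (MNT >10 to <20). The documents do not give *s*, so it is assumed to be 10–50%. From 0.83 = (1 − s) × 0.90 + s × x, the rate in the band is x = 0.90 − 0.07/s.

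**3. Variance explained.** Assume vAUC is 0 in the uninfected, with mean 1 and CV 0.3 in the infected.
- Total variance = 0.83 × (1 + 0.3²) − 0.83² = 0.9047 − 0.6889 = 0.2158.
- Variance due to band = s(1 − s)(0.07/s)².
- R² is the second divided by the first. The SE falls by 1 − √(1 − R²), and the equivalent sample-size gain is 1/(1 − R²) − 1.

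| s | Implied rate in band | R², infection | R², vAUC | SE reduction, vAUC | Equivalent extra participants |
|---|---|---|---|---|---|
| 0.10 | 20% | 0.313 | 0.204 | 10.8% | 26% |
| 0.20 | 55% | 0.139 | 0.091 | 4.6% | 10% |
| 0.30 | 67% | 0.081 | 0.053 | 2.7% | 6% |
| 0.50 | 76% | 0.035 | 0.023 | 1.1% | 2% |

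The column for infection is not the relevant one, because the models analyse AUCs. Changing the assumed CV from 0 to 0.5 moves the SE reduction from 7.2% to 2.9% at s = 0.20, and from 1.8% to 0.7% at s = 0.50. Nothing comparable can be computed for the symptom score.

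**4. Simulation of the SAP's ANCOVA.** Settings: N = 134, 80:54, eight cohorts, CV 0.3, 3,000 runs per case, with and without a two-level MNT term. For s = 0.10, 0.20, 0.30 and 0.50:
- band spread evenly over cohorts: SE ratio 0.90, 0.96, 0.98, 0.99;
- band confined to the later half of cohorts: 0.91, 0.97, 0.99, 1.00.

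**5. Late entry with a smaller share.** The band was admitted only from version 5.0 (10 July 2019). Vaccination began in April 2019, in seven cohorts about three weeks apart (SAP 4.6.1). If that schedule held from early April, about two of the seven cohorts came after the change. Suppose a fraction *f* of cohorts is late, a share *p* of those participants is in the band, and the implied rates from step 2 are kept (x at s = p).
- Within-cohort variance is f × 0.2158 + (1 − f) × 0.171, where 0.171 = 0.90 × 1.09 − 0.90². The band contributes f × p(1 − p)(0.07/p)².
- f = 2/7: total 0.1838. Band 0.0056 at p = 0.2 and 0.0014 at p = 0.5. SE reduction 1.5% and 0.4%.
- f = 3/7: total 0.1902. Band 0.0084 and 0.0021. SE reduction 2.2% and 0.6%.

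**6. Chance imbalance.** The SD of the difference in band share between arms is √[s(1 − s)(1/80 + 1/54)]. At s = 0.30 this is √0.21 × 0.1761 = 0.081. Multiplied by 0.233/0.83, it shifts mean vAUC by 2.3% per SD, or 4.4% at 1.96 SD. At s = 0.20 and 0.50 the 1.96-SD shifts are 5.8% and 2.9%. The target difference is 22%.

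**7. Cost.** The ANCOVA uses 11 parameters (intercept, treatment, sex, time, seven cohort contrasts), leaving 134 − 11 = 123 residual df. One more term leaves 122. If titre is useless, the SE rises by about √(123/122) − 1 = 0.4%.

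**The case against.** The case for leaving the models alone is a fair one.

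- **The rates do not establish prognosis.** A reader might infer from 90% and 83% that the added band must have a clearly lower take rate. That follows only if both figures come from one nested data set without sampling error. They are approximate, have no denominators or intervals, and both include ongoing studies. No rate is given for the band itself, and Protocol 1.1 calls the effect minimal. This stands.
- **The split is close to assay noise.** The version 5.0 rationale describes the added value as the geometric mean of one duplicate reading 10 and one reading 20. The titre may also be months old at challenge. This stands and could shrink the gain.
- **Challenge cohort already absorbs part of it**, because the band entered by calendar time. This is true in part. Cohort captures only between-cohort differences, and SAP 2.1.3 drops it if the maximum VIF exceeds 10.
- **The models are supportive.** The powered analysis is the unadjusted Mann-Whitney test, and treatment is randomised. A reader might infer that the primary result is weakened or the estimate biased. Neither is so: omitting a baseline covariate here costs precision, not validity. Nor is the ANCOVA the only adjusted estimate, since the MMRM also gives adjusted means and a multiple-imputation ANCOVA is listed.
- **Titres may sit elsewhere.** A result from another study need not be repeated, so a value in the analysis data set for everyone has to be confirmed. This stands.

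None of these points shows that the covariate would do harm.

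**Conclusion.** The omission is certain: screening MNT is in neither the text nor the code of the adjusted models, although it is a baseline value that entry depends on. Its inclusion is a free improvement.

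The gain is probably small. For vAUC the SE falls by roughly 1–5% if 20–50% of participants are in the added band, by about 0–3% if the band entered only in the last few cohorts, and by nearly nothing if titre is not prognostic between 10 and 20. The 11% case needs a rare band with a 20% attack rate, which fits poorly with the protocol's claim of a minimal effect. These figures rest on an assumed band share, an assumed CV of 0.3 among the infected, zero vAUC in the uninfected and both attack rates at face value. Adjustment would also correct chance imbalance in titre, worth a few per cent of mean vAUC under the same assumptions.

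Confidence is high on the omission and moderate to low on the size of the gain. Separately, the attack rates of 90% and 83% and the statement of a minimal effect should be reconciled.

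**What to change.** 1. In SAP 2.1.3 and the code in 9.1, add screening MNT to the ANCOVA and both MMRMs, either as log titre or as a two-level factor (≤10 versus >10 to <20). Use the pre-vaccination value. The Day -1 titre is measured after randomised vaccination and should not be used.
2. Confirm that titres taken from other protocols are in the analysis data set.
3. Make the change before the topline results, which SAP 1.5 presents with group-level unblinding ahead of database lock. If it comes later, keep the planned models and report the MNT-adjusted ones as a labelled sensitivity analysis.
4. In the protocol, reconcile the statement of a minimal effect in 1.1 with the two attack rates in 1.1 and 3.2, giving denominators and, if available, the rate in the added band.

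The cost is one covariate in text and code, 1 degree of freedom and a data check, with no new sampling. The primary Mann-Whitney analysis stays as it is.
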